## **MATERIAL AND METHODS**

### **1.1 Definition of study subjects**

The inclusion criteria: being over 18 years of age, ASA physical status I – III and having been scheduled for shoulder arthroscopy surgery.

The exclusion criteria: any contraindication for performing regional anesthetic techniques (infection at the puncture point, alteration of hemostasis, allergy to local anesthetics, patient refusal to participate in the study, inability to evaluate postoperative pain, known neuropathy of the operated limb and patients who required conversion to open surgery).

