## PROTOCOL

All patients will be trained preoperatively in pain assessment using a Numerical Rating Scale (NRS) from 0 (absence of pain) to 10 (maximum pain endured). All patients will receive the same anesthesia and analgesia protocol; fentanyl, propofol and rocuronium prior to intubation.

Anesthetic maintenance with 1 MAC of sevoflurane and boluses of muscle relaxant and fentanyl if there is an increase >20% in blood pressure or above baseline heart rate. The anesthetic protocol will include analgesia with 1 g of paracetamol and 50 mg of dexketoprofen every 8 hours and a bolus of 0.1 mg/kg of intravenous dexamethasone. When the patient reports an NRS > 3 and functional impact, intravenous morphine will be administered at a dose of 0.04 mg/kg every 10 minutes until NRS < 3 in the PACU and tramadol 1 mg/kg in the ward. The nursing staff and the anesthesiologist in charge of the PACU will be blind to the block received by the patient in each study group.

Before general anesthesia, patients will be assigned to one of the study groups depending on the anesthesiologist responsible for performing the blocks.

**SHAC + SSN Group (anterior approach):** with the patient in the supine position and the arm placed in abduction and slight external rotation the ultrasound probe will be positioned in the transverse axis between the coracoid process and the humeral head. After identifying the tendon of the subscapularis muscle, a puncture will be performed in a lateral to medial plane and the local anesthetic will be deposited at two levels; one deep to the subscapularis tendon at the pericapsular level of the glenohumeral joint (5 ml of ropivacaine 0.2%), and another in withdrawal at about the level of the fascia that separates the subscapularis and deltoid muscles at a more superficial level (10 ml of 0.2% ropivacaine). Subsequently, the ultrasound probe will be positioned in the transverse axis at level with the neck to locate the suprascapular nerve through an anterior approach as it ran beneath the omohyoid muscle. After hydrodissecting the correct plane with saline solution 5 ml of 0.2% ropivacaine will be administered, depositing the local anesthetic under the lower belly of the omohyoid muscle.

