**SSN + AN group (posterior approach):** with the patient in a sitting position and the arm placed in a neutral position, with slight internal rotation supported on the abdomen, the ultrasound probe will be positioned in the supraspinous fossa and a first puncture of the suprascapular nerve will be performed posteriorly, level with the supraspinous fossa. Next, the probe will be positioned at the level of Velpeau's quadrilateral and a second puncture of the axillary nerve will be performed, taking the posterior humeral circumflex artery as a sonoanatomical reference in the plane of intersection formed by the deltoid, triceps brachii, and teres minor muscles. After locating the planes by hydrodissection with saline solution 10 ml of 0.2% ropivacaine will be administered to each of the nerves.

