## **JUSTIFICATION OF SAMPLE SIZE**

Because no work of this nature has been carried out previously, a sample size calculation will be not performed and all patients who underwent surgery in the 12 months that the study data collection will last were consecutively included in the study.

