## **VARIABLES EVALUATED**

The main variable will be the measurement of pain intensity according to the NRS at different times: preoperative and at the 1st, 2nd, 12th and 24th postoperative hours. As secondary variables, postoperative opioid requirements will be assessed in the form of intravenous morphine, measured in mg (only during the 2 hours of the patient's stay in the Postanesthesia Care Unit), and tramadol (mg) up to 24 hours postoperatively.

The degree of sensory block will be also assessed by a cold sensitivity test with a cotton swab dipped in cold water applied to the skin of the upper third of the arm, which will be graded with a sensitive scale going from 0 to 2 (2 being normal sensitivity to cold, 1 hypoesthesia and 0 anesthesia). The degree of motor block upon arrival at the PACU will be assessed by the movement of the arm using a simple numerical scale (0 = cannot raise the extended arm  $> 45^\circ$  and 1 = can raise the extended arm  $> 45^\circ$ ), the ease of performance of the corresponding anesthetic technique by the anesthesiologist using a simple verbal scale (easy/medium difficulty/difficult), the appearance of adverse effects (postoperative nausea and/or vomiting, hematoma, pruritus, urinary retention), the degree of patient satisfaction (very satisfied, satisfied or dissatisfied) and the notification of complications related to the anesthetic techniques performed.

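### Conversion to open surgery is listed as an exclusion criterion but occurs after group assignment, so, with no retention rule, blocked patients drop out of the technique and safety summaries

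*Combined protocol and SAP*

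**What the plan says.** All references are to the combined protocol and SAP.

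- **Eligibility (section 1.1, Definition of study subjects).** A patient qualifies by "having been scheduled for shoulder arthroscopy surgery", together with age and ASA status. The exclusion list, which otherwise reads as conditions present before surgery, ends with "known neuropathy of the operated limb and patients who required conversion to open surgery".
- **Assignment (PROTOCOL).** "Before general anesthesia, patients will be assigned to one of the study groups depending on the anesthesiologist responsible for performing the blocks".
- **Block (PROTOCOL).** The time of the block relative to surgery is not stated outright. The posterior block is done "with the patient in a sitting position and the arm placed in a neutral position".
- **Outcomes (VARIABLES EVALUATED).** Besides NRS and opioid use, the plan records sensory block, "The degree of motor block upon arrival at the PACU", "the ease of performance of the corresponding anesthetic technique by the anesthesiologist", adverse effects, satisfaction and "the notification of complications related to the anesthetic techniques performed".
- **Analysis (STATISTICAL ANALYSIS PLAN).** The section names tests and software. It defines no analysis population, has no rule for data from patients excluded after the block, and does not ask for conversions by group.

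**The concern.** An eligibility criterion should be decidable when the patient enters the study. This one depends on an event that follows assignment and, almost certainly, the block. A patient can be scheduled for arthroscopy, meet every inclusion criterion, be assigned and blocked, and then leave the study because of what happened in the operation.

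The loss matters most for the outcomes that describe the block itself. How easy the block was to perform is settled once it has been performed. A complication of the block may already exist when the surgeon converts. Sensory and motor block and adverse effects can still be recorded after an open procedure. If these patients are removed, the ease ratings and complication rates no longer describe everyone who received the block. The background section says that only anatomical studies and small case series have been published on SHAC, so complete technique and safety data are a large part of what this study can add.

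**Working it through.** The plan states no figure that depends on this point, so there is nothing to reproduce. The check is first the order of events, then an illustration of size with assumed values.

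**Order of events**

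| Step | When | Basis |
|---|---|---|
| Eligible as scheduled for arthroscopy | Before surgery | Section 1.1, explicit |
| Group assigned | Before general anesthesia | PROTOCOL, explicit |
| Block given, ease of technique fixed | Before surgery | Inferred |
| Conversion to open surgery | During surgery | By definition |
| Motor block tested | PACU arrival | VARIABLES EVALUATED, explicit |

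The inference in the third row rests on three facts: assignment precedes general anesthesia and depends on who performs the blocks; the posterior block is done sitting, which suggests an awake patient; and motor block is assessed on PACU arrival, so the block has been given by then. Even without this inference, the exclusion acts after assignment.

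**Patients affected.** The documents give no conversion rate or group size. Assume a conversion share of 1–5% and 50–100 patients per group.

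- Low end: 0.01 × 50 = 0.5 patients per group.
- High end: 0.05 × 100 = 5 patients per group.

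**Complication rate.** If one deleted patient had a complication, the observed rate changes by about 1/100 to 1/50, or 1 to 2 percentage points. That is conditional on the event. With an assumed complication rate of 5%, the expected number of events lost per group is 0.5 × 0.05 = 0.025 to 5 × 0.05 = 0.25. If complications are unrelated to conversion, the expected rate does not change, because numerator and denominator fall in proportion.

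**Mean NRS.** Let c be the share of a group that converts and d the mean NRS difference between converted and unconverted patients. Excluding converted patients lowers that group's mean by c × d.

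- With c = 1% and d = 1: 0.01 × 1 = 0.01 points.
- With c = 10% (a deliberately wide upper value) and d = 3: 0.10 × 3 = 0.30 points.

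If d is the same in both groups, the between-group difference shifts by (c1 − c2) × d. With equal conversion this is 0. With rates 5 percentage points apart and d = 1 to 3, it is 0.05 × 1 = 0.05 to 0.05 × 3 = 0.15 points.

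**The case against.** The strongest defence is that the title, background and hypotheses all concern pain after arthroscopic shoulder surgery. In a non-randomized study there is no randomization to preserve, so restricting the NRS and opioid comparison to completed arthroscopies is defensible. This stands for pain and opioid use. It does not reach ease of technique, block assessment or complications of the block, which do not depend on the operation staying arthroscopic.

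It can also be said that the plan never orders these data to be deleted, and that the complication variable is not limited to unconverted patients. That is true. The loss follows from listing conversion as an exclusion while giving no retention rule. The documents do not state it in so many words.

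Four stronger readings are tempting and are not supported:

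- **A contradiction with the sample-size section.** That section says "all patients who underwent surgery in the 12 months that the study data collection will last were consecutively included in the study", which may look incompatible with any later removal. The abstract, however, limits consecutive recruitment to patients who meet the criteria, and consecutive inclusion is ordinarily subject to eligibility. Read literally, every exclusion would contradict that sentence.
- **Outcome-dependent exclusion through the criterion on inability to assess pain.** A reader might infer that it could be applied after surgery, for instance to a sedated patient. Nothing in the documents says so, and its place in a loosely worded list is not evidence of timing.
- **A biased pain comparison because the block influences conversion.** No section links block type to conversion. If conversion differed through surgeon, centre or case mix, that would be confounding from assignment by anesthesiologist, which keeping converted patients would not cure.
- **Converted patients must be in the main NRS analysis.** Including them fits everyone who was blocked; leaving them out fits the arthroscopy question. This is a trade-off.

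**Conclusion.** The concern holds in a limited form. An intraoperative event is used as an eligibility criterion after group assignment and, by strong inference, after the block. As written, this takes blocked patients out of technique and safety summaries to which they validly belong. Under the assumed rates and group sizes, the number is about 0.5 to 5 per group. The distortion of mean NRS is probably small, and zero if conversion rates and the pain difference are the same in both groups. A complication rate changes materially only if a converted patient had a complication. In a small study, though, that could be the only such event. The case for changing the plan rests on complete description of the block and on the very low cost, not on a demonstrated bias in the pain comparison.

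**What to change.** 1. In section 1.1, remove conversion from the exclusion criteria and state that eligibility closes when the group is assigned.
2. State that every patient who received a block stays in the summaries of ease of technique, sensory and motor block, adverse effects and complications.
3. Report the number of conversions in each group. The recruitment section fills each group to a number it does not give, so converted patients could otherwise be replaced without trace.
4. Present the NRS and opioid comparison both with and without converted patients, and state in advance which is primary. Either choice is defensible.

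The cost is a few sentences of protocol wording and one extra analysis. If the version with converted patients is made primary, its NRS values may be slightly more variable because of a few open procedures.

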## **RECRUITMENT AND RECRUITMENT OF PARTICIPANTS**

The anesthesiologist responsible for the operating room performed both the block of the anterior capsule of the shoulder and the suprascapular nerve via the anterior route and the blocks of the suprascapular and axillary nerves via the posterior route until the number of patients established in each of the groups is reached.

## **JUSTIFICATION OF SAMPLE SIZE**

Because no work of this nature has been carried out previously, a sample size calculation will be not performed and all patients who underwent surgery in the 12 months that the study data collection will last were consecutively included in the study.

## **VARIABLES EVALUATED**

The main variable will be the measurement of pain intensity according to the NRS at different times: preoperative and at the 1st, 2nd, 12th and 24th postoperative hours. As secondary variables, postoperative opioid requirements will be assessed in the form of intravenous morphine, measured in mg (only during the 2 hours of the patient's stay in the Postanesthesia Care Unit), and tramadol (mg) up to 24 hours postoperatively.

The degree of sensory block will be also assessed by a cold sensitivity test with a cotton swab dipped in cold water applied to the skin of the upper third of the arm, which will be graded with a sensitive scale going from 0 to 2 (2 being normal sensitivity to cold, 1 hypoesthesia and 0 anesthesia). The degree of motor block upon arrival at the PACU will be assessed by the movement of the arm using a simple numerical scale (0 = cannot raise the extended arm  $> 45^\circ$  and 1 = can raise the extended arm  $> 45^\circ$ ), the ease of performance of the corresponding anesthetic technique by the anesthesiologist using a simple verbal scale (easy/medium difficulty/difficult), the appearance of adverse effects (postoperative nausea and/or vomiting, hematoma, pruritus, urinary retention), the degree of patient satisfaction (very satisfied, satisfied or dissatisfied) and the notification of complications related to the anesthetic techniques performed.

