## BACKGROUND AND JUSTIFICATION OF THE PROJECT

Arthroscopic shoulder surgery is related to a high incidence of postoperative pain, being rated as intense by 45% of patients in the immediate postoperative period (1). The management of these patients can be complex due to the high incidence of preoperative pain and its variability during the postoperative period, which is higher in patients undergoing rotator cuff repair surgery (2).

It is crucial to ensure adequate postoperative pain control in this type of intervention, especially in the context of major outpatient surgery. Adequate postoperative pain control can have several benefits, such as reducing hospital stay (3), accelerating postoperative rehabilitation (4), and improving long-term outcomes (5).

The PROSPECT guideline for rotator cuff repair surgery recommends associating a regional analgesic technique with a multimodal pharmacological approach to pain. (6).

Traditionally, the interscalene block has been considered the gold-standard for analgesia in shoulder surgery; However, its possible serious complications limit its use. Currently, most anesthesiologists choose to perform more distal peripheral nerve blocks of the brachial plexus (upper trunk block, supraclavicular block, infraclavicular block at the costoclavicular level, axillary nerve block...) which, although highly effective, continue to cause impairment. prolonged motor activity and are not free of complications (phrenic paralysis, transient nerve injuries, inadvertent vascular punctures...) (7).

Shoulder anterior capsular block (SHAC) has recently been described. It is a fascial block of the anterior capsule of the shoulder that aims to avoid motor impairment while maintaining optimal analgesic efficacy (8)(9). However, so far only anatomical and descriptive studies of small case series have been published. Therefore, this research work, with the objective of comparing the postoperative analgesic effectiveness of two regional analgesic techniques: the SHAC block associated with the suprascapular nerve block performed anteriorly vs. suprascapular and axillary nerve blocks performed posteriorly in operated patients. of the shoulder via arthroscopic procedures that cause intense postoperative pain.

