## **STUDY TYPE**

An observational study of paired cohorts, not randomized, is designed in two hospitals in northern Spain in the period between october 2023 and september 2024.

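### The listed variables include no baseline or surgical covariate except preoperative NRS, so in this non-randomised comparison imbalance on other prognostic factors cannot be assessed or adjusted for unless those factors are added to the dataset

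*Combined protocol and SAP*

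**What the plan says.** **Design and allocation.** STUDY TYPE: "An observational study of paired cohorts, not randomized, is designed in two hospitals in northern Spain". No pairing variable is named anywhere. PROTOCOL: "patients will be assigned to one of the study groups depending on the anesthesiologist responsible for performing the blocks". The recruitment section reads differently. There, the anesthesiologist in charge of the operating room performs both techniques until each group reaches its number.

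**Variables.** VARIABLES EVALUATED opens with "The main variable will be the measurement of pain intensity according to the NRS at different times" and gives those times in full: "pain intensity according to the NRS at different times: preoperative and at the 1st, 2nd, 12th and 24th postoperative hours". The secondary variables start with "postoperative opioid requirements will be assessed in the form of intravenous morphine, measured in mg" in the PACU, plus tramadol to 24 hours. The rest are sensory and motor block, ease of technique, adverse effects, satisfaction and complications. Age, sex, weight, ASA class, prior opioid or other analgesic use, procedure, repair extent, hospital and operator are not listed.

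**Eligibility.** Section 1.1 admits patients on "being over 18 years of age, ASA physical status I – III and having been scheduled for shoulder arthroscopy surgery". The exclusions end with "inability to evaluate postoperative pain, known neuropathy of the operated limb and patients who required conversion to open surgery", and prior opioid use is not among them. The abstract's study population is limited to unilateral rotator cuff repair, whereas section 1.1 admits any shoulder arthroscopy.

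**Analysis.** The STATISTICAL ANALYSIS PLAN names Student's t, Mann-Whitney, chi-square, Fisher and Kruskal-Wallis with Bonferroni, at p below 0.05. It plans no matching, stratification, regression or propensity score.

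**The concern.** When the operator determines the group, nothing in the design balances the two groups on factors that drive pain or opioid need. The background section itself says that such factors matter in this population: "The management of these patients can be complex due to the high incidence of preoperative pain and its variability during the postoperative period". It adds that the problem is greater after rotator cuff repair.

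If one group holds more patients already on opioids, or more extensive repairs, that difference passes directly into postoperative NRS, morphine and tramadol. An unadjusted test would credit it to the block. A reader of the results could neither see the imbalance nor correct for it, because the listed variables do not contain the factors. Recruiting more patients does not help: the bias stays the same while the standard error shrinks, so a false finding becomes more likely.

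This is a separate matter from whether the analysis uses the preoperative NRS it already has. A covariate has to be in the dataset before any model can use it.

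**Working it through.** The plan states no sample size, effect or SD (JUSTIFICATION OF SAMPLE SIZE says that no calculation is made), so there is no figure of its own to reproduce. The check has two parts: a reading of the documents, and an illustration of size in which every numerical input except the 0.05 level is assumed.

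**1. Reading.** Every section was searched for baseline variables, exclusions and adjustment.
- Listed before treatment: preoperative NRS only.
- Known in care but not listed: age, ASA class and scheduled procedure (needed for eligibility), and weight (needed for per-kilogram dosing).
- Neither listed nor implied by eligibility or dosing: sex, prior opioid or analgesic use, repair extent. Hospital and operator are part of the design but are not listed.
- Adjustment planned: none.

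**2a. Bias from one unlisted factor.** Bias = difference in prevalence × effect of the factor.
- Assumed: 25% versus 10% prior opioid users, effect 2 NRS points. Bias = 0.15 × 2 = 0.30 points.
- Assumed effect of 100 mg on tramadol: 0.15 × 100 = 15 mg.

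**2b. Effect on the false-positive rate.** Assume SD 2, no true difference and a two-sided test at 0.05 (the plan does not state sidedness). SE = 2 × √(2/n), and rate = 1 − Φ(1.96 − bias/SE) + Φ(−1.96 − bias/SE).

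| n per group | SE | 0.30/SE | Rate, bias 0.30 |
|---|---|---|---|
| 30 | 0.516 | 0.58 | 9% |
| 40 | 0.447 | 0.67 | 10% |
| 50 | 0.400 | 0.75 | 12% |
| 100 | 0.283 | 1.06 | 19% |

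Range over other assumed scenarios, at 30 / 50 / 100 per group:
- 10-point imbalance, 1-point effect (bias 0.1): 5.4% / 5.7% / 6.4%.
- 20-point imbalance, 2-point effect (bias 0.4): 12.1% / 17.0% / 29.3%.
- 30-point imbalance, 2-point effect (bias 0.6): 21.3% / 32.3% / 56.4%.

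**2c. Chance imbalance.** Assume 40 per group and 20% prevalence in both. A difference of 15 points or more means at least 6 patients out of 40. The exact binomial probability is 12.3%. The uncorrected normal approximation, with SD = √(2 × 0.2 × 0.8/40) = 0.089, gives about 9% and is too low here because the count is discrete. Assignment by operator or hospital can add systematic imbalance to this.

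**2d. What preoperative NRS can remove.** A factor that differed between groups by 0.3 SD and affected the outcome was simulated. Adjusting for preoperative NRS alone removed about 4%, 24% and 62% of the confounding when the factor's correlation with preoperative NRS was 0.2, 0.5 and 0.8. The removed share is roughly the squared correlation.

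**The case against.** **A reader might infer that imbalance can never be shown or removed by any later analysis.** The documents do not support that. Preoperative NRS is collected, so imbalance in baseline pain, the factor that the background stresses, can be shown and adjusted for. Doing so also removes some confounding by related factors (step 2d). Age and ASA class must be known at eligibility, and participants carry a code, so further fields might be retrieved. How far is unclear: the confidentiality section describes the data as both coded and untraceable, and the ethics section treats the study as an anonymous survey. That uncertainty is a reason to specify the fields before collection. It does not show that retrieval is impossible.

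**A reader might infer that no patient characteristics will be collected.** That goes too far as well. The section lists outcomes, and the data-collection form is not among the documents available. What can be said is that the plan lists no such variable and assigns none to the analysis.

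**A reader might infer that admitting opioid users is itself an error.** It is a legitimate choice in a study of consecutive patients in usual practice. The gap is that prior use is not a listed variable.

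**The size is assumed.** This objection stands in full. No prevalence, effect, SD or group size comes from the documents, and a bias of 0.30 points is modest. It limits what can be said about magnitude, but the gap in the variable list remains.

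**Conclusion.** The point holds in this form: the plan lists no baseline or surgical covariate except preoperative NRS, leaves prior opioid use neither excluded nor listed, and tests two operator-determined groups without adjustment. On the unlisted factors, imbalance cannot be assessed or adjusted for unless they are added. Adjusting for preoperative NRS would usually be a partial remedy only.

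The size cannot be fixed from the documents. Across the assumed scenarios, the false-positive rate ranges from barely above 5% to over 50%. The central illustration roughly doubles it at 40 per group. These rates rest on an SD of 2, equal groups and a single unlisted factor. The plan should be changed, since the remedy is cheap and case mix cannot otherwise be told apart from a block effect.

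**What to change.** 1. In VARIABLES EVALUATED, add from existing anesthetic and surgical records: age, sex, ASA class, preoperative opioid use, other preoperative analgesic use, procedure and repair extent (for example tear size or number of tendons repaired), hospital and operator.
2. In the STATISTICAL ANALYSIS PLAN, tabulate these and preoperative NRS by group with standardised differences. Take the main comparison of NRS and of opioid consumption from a model with a small set of covariates fixed in advance: preoperative NRS, prior opioid use, repair extent and hospital. Keep the unadjusted tests as supporting results.
3. Reconcile the PROTOCOL and recruitment sections on whether each anesthesiologist gives one technique or both. If only one, state as a limitation that operator and block cannot be separated by any analysis.

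Cost: a few fields per patient and some wording in the analysis section. Since the ethics section sends protocol modifications for re-evaluation, this one would go there too. The downside is that the covariate set must stay small if the groups are small, and no model removes confounding by factors that remain unrecorded.

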### **• MAIN AND SECONDARY OBJECTIVES**

#### **Main:**

The measurement of pain intensity according to the numerical rating scale (NRS) at different times: preoperative and at the 1st, 2nd, 12th and 24th postoperative hours.

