### **GOALS:**

- **Main objective**

The measurement of pain intensity according to the NRS at different times: preoperative and at the 1st, 2nd, 12th and 24th postoperative hours.

- **Secondary objectives**

Postoperative opioid consumption and comparison of total cumulative consumption between the two groups.

It will also evaluated the degree of sensory and motor block, the easy of performance of the anesthetic technique, the degree of patient satisfaction and the record of short-term complications (first 24 hours post-intervention): hematoma, pruritus, nausea and/or vomiting.

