## **STATISTICAL ANALYSIS PLAN**

Continuous quantitative variables will be expressed as mean and standard deviation and the results will be contrasted using the Student's T test if normality criteria will be met, failing which they will be expressed as median and range and contrasted using the Mann Whitney's U. The qualitative variables will be expressed in absolute numbers and relative frequencies and the results of both groups will be contrasted using the Chi square. In addition, Fisher's test will be applied when necessary. Normality tests will be conducted for all continuous quantitative variables. The Kruskal-Wallis technique will be also employed with post-hoc application of the Bonferroni test for the analyses. The data will be processed using SPSS software version 19.0 (IBM Corporation, Armonk, NY, USA), assuming a p-value below 0.05 as significant.

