## **ETHICAL-LEGAL ASPECTS**

All data collected will be managed in accordance with the regulations established by Organic Law 3/2018, of December 5, on the Protection of Personal Data and guarantee of digital rights; such as 14/2007 of July 3, on Biomedical Research; such as the Standards of Good Clinical Practice, Declaration of Helsinki, as well as the Oviedo Convention.

The study protocol and all associated documentation will be submitted for evaluation to the CAEI of Galicia. Any modification to the initial approved protocol will be sent for re-evaluation.

Researchers assume the commitment to make public the results of their research, whether positive or negative.

Since this is an anonymous survey, informed consent will not be necessary.

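### The main pain outcome is NRS at five times, with no primary hour or summary and no error control tied to those times, so up to 18.5% false positives are possible if any postoperative hour below 0.05 counts

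*Combined protocol and SAP*

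**What the plan says.** Three places define the main outcome. In the abstract, the main objective under MAIN AND SECONDARY OBJECTIVES begins "The measurement of pain intensity according to the numerical rating scale (NRS) at different times" and lists the times. GOALS gives "The measurement of pain intensity according to the NRS at different times: preoperative and at the 1st, 2nd, 12th and 24th postoperative hours". VARIABLES EVALUATED makes the main variable "pain intensity according to the NRS at different times: preoperative and at the 1st, 2nd, 12th and 24th postoperative hours". None of them names a decisive hour, a summary over hours, or the number of hours that must differ.

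BACKGROUND AND JUSTIFICATION OF THE PROJECT states a comparative aim: "with the objective of comparing the postoperative analgesic effectiveness of two regional analgesic techniques".

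STATISTICAL ANALYSIS PLAN compares continuous variables by t test or Mann-Whitney, "assuming a p-value below 0.05 as significant". It then adds: "The Kruskal-Wallis technique will be also employed with post-hoc application of the Bonferroni test for the analyses". That sentence names no variable, grouping factor, family of comparisons or divisor. No summary across times and no repeated-measures model is mentioned.

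JUSTIFICATION OF SAMPLE SIZE contains no calculation, so no design target shows which hour was meant. On allocation, PROTOCOL says that "patients will be assigned to one of the study groups depending on the anesthesiologist responsible for performing the blocks".

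**The concern.** One comparative question has four postoperative readings that could answer it, plus any summary of them, and the plan does not say which decides. It leaves open whether one significant hour would be a positive main result, and whether Bonferroni was meant to cover the hours. The hour or summary to emphasise can therefore be chosen after the data are seen. Listing all the times in advance and committing to publish limit the hiding of results, but they do not limit selective emphasis.

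The preoperative reading sits inside the main variable although it cannot measure postoperative analgesia. Its natural use, as a baseline covariate, is not planned.

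**Working it through.** **Inputs from the documents.** Four postoperative times (1, 2, 12 and 24 h), two groups and a 0.05 threshold. Sidedness is not stated, so two-sided is assumed. The documents give no group size, standard deviation, effect size or correlation between hours, so those below are assumptions. The plan states no family-wise error rate, so there is no figure to reproduce.

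**1. What the Kruskal-Wallis sentence can do.** If its factor is the study group, there are two levels and one pair, so a post-hoc Bonferroni has nothing to correct. With two groups the test is Mann-Whitney without continuity correction; in a numerical example both gave p = 0.009765. If its factor is time within patients, the readings are not independent and the test is unsuitable. The text does not say which is meant.

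**2. Error rate if any one of four hours counts.** For independent tests:

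- at 0.05 each: 1 − (1 − 0.05)^4 = 1 − 0.8145 = 18.5%
- at 0.0125 each (0.05/4): 1 − (1 − 0.0125)^4 = 1 − 0.9509 = 4.9%

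For correlated tests, take equicorrelated normal statistics with correlation ρ and two-sided critical value c (1.960 at 0.05). Then

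P(at least one) = 1 − ∫ φ(t) [Φ((c − √ρ t)/√(1 − ρ)) − Φ((−c − √ρ t)/√(1 − ρ))]^4 dt.

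| ρ (assumed) | each at 0.05 | each at 0.0125 |
|---|---|---|
| 0 | 18.5% | 4.9% |
| 0.3 | 17.4% | 4.7% |
| 0.5 | 15.6% | 4.3% |
| 0.7 | 13.0% | 3.7% |
| 0.9 | 9.4% | 2.6% |

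As ρ approaches 1 the first column tends to 5%.

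**3. Checks.** With correlation decaying over successive hours (lag-one 0.3 to 0.9), the uncorrected rate runs from 17.8% to 10.4%. Mann-Whitney on simulated whole-number 0–10 scores, 20 to 80 per group, gave 17.3–19.1% at ρ = 0, 14.7–16.6% at 0.5 and 10.2–10.7% at 0.9. At 0.0125 it gave 2.5–4.9%. Each cell had 4,000 runs, so the standard error near 18.5% is √(0.185 × 0.815/4000) = 0.6 percentage points; 19.1% is consistent with 18.5%.

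**4. What the remedies do.** Suppose the mean over four hours is primary and the single hours are Holm-adjusted but claimable whatever the primary shows. The chance of any false claim is then 8.7% at ρ = 0 and 5.1% at 0.9. If the hours can be claimed only after a significant primary, it is 5.0% throughout.

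The choice of summary matters. A mean puts 2/4 = 50% of the weight on 1 and 2 h. A trapezoidal area under the curve from 1 to 24 h has weights 0.5/23, 5.5/23, 11/23 and 6/23, so 6/23 = 26% falls on those hours. Power for an assumed 50 per group, 0.5 SD difference and ρ = 0.5, without baseline adjustment:

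| Difference present at | mean | area under curve | at least one Holm-adjusted hour |
|---|---|---|---|
| 1 and 2 h only | 35% | 12% | 68% |
| 12 and 24 h only | 35% | 61% | 68% |
| all four hours | 89% | 86% | 80% |
| early and late, opposite signs | 5% | 31% | 97% |

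A single named hour has 71% power if the difference is present at that hour and 5% if it is not.

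**The case against.** The strongest reply is that this is a non-randomised observational study whose main objective is worded as a measurement. It has no formal null hypothesis and no power calculation, so a confirmatory error rate asks more than the study claims. Part of that stands and limits how serious the point is. It does not remove it, because the plan also states a comparative aim and a significance threshold.

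Four stronger readings are tempting, and the documents do not support them.

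- *That the plan has no multiplicity control.* Bonferroni is named. What is missing is any link to the NRS times.
- *That the Kruskal-Wallis sentence certainly corrects nothing.* This holds if the factor is the two study groups. The factor is not named and could be time, the anesthesiologist, or a three-level variable such as ease of performance or satisfaction. Only its undetermined scope can be shown.
- *That the study's false-positive rate is 9–19%.* Those ends correspond to assumed correlations of 0.9 and 0. Zero correlation is hard to credit for repeated scores in one patient, so 18.5% is a ceiling, not an expected value. The inflation arises only if each hour is tested at 0.05 and any one suffices, which the plan neither states nor excludes.
- *That there are five tests, giving 22.6% at zero correlation.* A preoperative difference would be read as baseline imbalance, not as a false claim about a block. Four is the right count.

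**Conclusion.** The concern holds in limited form and should be fixed. The plan does not determine which NRS comparison answers the main objective, and no error control is tied to the NRS times. The size depends on a decision rule the plan leaves open. The uncorrected any-hour rule has a multiplicity error between 5% and 18.5% according to correlation; Bonferroni over the four hours holds it to at most 4.9%.

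The arithmetic is secure given two-sided tests and groups that do not differ apart from the block. Allocation by anesthesiologist does not ensure the latter, so none of these percentages is the study's actual false-positive rate; confounding is a separate problem that no multiplicity rule removes. Nothing here makes the data unusable.

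**What to change.** Amend MAIN AND SECONDARY OBJECTIVES, GOALS, VARIABLES EVALUATED and STATISTICAL ANALYSIS PLAN together.

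1. List preoperative NRS as a baseline covariate, not an outcome, and adjust the main comparison for it.
2. Choose one option before NRS results by group are seen. If they have been seen, label the choice post hoc.
   - **A. One primary comparison.** Name one postoperative hour, or one summary over 1, 2, 12 and 24 h with its weights, tested at two-sided 0.05. The other hours are secondary, Holm-adjusted, and claimed only if the primary is significant.
   - **B. Four co-equal hours.** Apply Holm, or Bonferroni at 0.0125, across exactly the four postoperative hours. This is the smaller change and suits the case where no hour or summary can be justified in advance.
3. Name the factor with three or more levels for which Kruskal-Wallis with Bonferroni is meant, or delete the sentence. Do not use it on repeated readings within patients.

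**Cost.** Text changes and no new measurements. ETHICAL-LEGAL ASPECTS requires resubmission: "Any modification to the initial approved protocol will be sent for re-evaluation". Under B, or for hours not named primary under A, a single p just below 0.05 no longer counts as a positive main result. Under A, a summary can miss a difference confined to early or late hours, and the hours then cannot be claimed. Under B, power is somewhat lower than with a summary when the difference is present throughout (80% against 86–89% in the illustration).
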